6.1.3 Product Storage and Stability

Vaccines, GLA-AF, and placebo will be stored at the site in a refrigerator at 2°C to 8°C until just prior to administration and will not be frozen; refrigerator temperature will be monitored continuously. All vaccine vials will be stored in the upright position.

6.2 Dosage, Preparation and Administration of Study Intervention/Investigational Product

Doses of *Na*-APR-1 (M74)/Alhydrogel[®] and *Na*-GST-1/Alhydrogel[®] administered without GLA-AF will be prepared by withdrawing appropriate volumes into syringes of appropriate size. The *Na*-APR-1 (M74)/Alhydrogel[®] plus GLA-AF formulations will be prepared by adding appropriate volumes of GLA-AF solution to vials of *Na*-APR-1 (M74)/Alhydrogel[®], or vice versa, within 24 hours of vaccination. Doses of the sterile saline control will be prepared by withdrawing the appropriate volume into syringes of appropriate size.

Vaccine doses will be administered by qualified study personnel (a study nurse or physician) in the deltoid muscle of the appropriate arm after disinfecting the skin with an alcohol swab and allowing it to dry.

6.3 Modification of Study Intervention/Investigational Product for a Participant

There will be no dose modifications. If a subject's second and/or third dose of study vaccination is deferred, it should be rescheduled to occur within the acceptable protocol-specified window for that visit. If this period elapses, the site must obtain prior approval from the Sponsor to administer the second and/or third study vaccination and the documentation of approval should be filed in the subject's chart. Subjects who do not receive the second and/or third study vaccination will be asked to return for safety assessments and for scheduled venous blood sample collections for immunogenicity testing and will be followed for the duration of the study.

Unblinding can occur upon request of the Independent Safety Monitor or the SMC at any time during the study.

6.4 Accountability Procedures for the Study Intervention/Investigational Product(s)

Study vaccines, GLA-AF, and sterile saline placebo supplies must be received by a designated person at the study site, handled and stored safely and properly, and kept in a secure location to which only the designated individuals have access. Study-site personnel are responsible for maintaining accurate records of the vaccine supplies (i.e., *Na*-GST-1/Alhydrogel[®], *Na*-APR-1 (M74)/Alhydrogel[®], the sterile saline placebo, and GLA-AF) received, the quantities administered to study subjects, and the amounts remaining at the conclusion of the study.

After administration of vaccine or GLA-AF doses, the empty or wasted vials will be accounted for and stored at the study site until monitoring by the study Sponsor or their designee. At the conclusion of the study, all used and unused *Na*-GST-1/Alhydrogel[®], *Na*-APR-1 (M74) /Alhydrogel[®], and GLA-AF vials will be returned to the Sponsor or destroyed on site upon direction from the Sponsor, or maintained at 2 to 8°C until further notice from the Sponsor regarding their disposition.

6.5 Assessment of Subject Compliance with Study Intervention/Investigational Product

Not Applicable.

6.6 Concomitant Medications/Treatments

Administration of any medications, therapies, or vaccines will be recorded on the appropriate data collection form. Concomitant medications will include all medications taken within the 30 days prior to enrollment, 28 days after each dose of study product, and for new-onset chronic medical conditions through the end of participation in the study for each subject. Prescription and over-the-counter drugs will be included as well as vitamins and supplements.

Use of new medication will prompt an evaluation for the presence of a new diagnosis of chronic medical disease or chronic medical condition.

Medications that might interfere with the evaluation of the investigational product should not be used unless absolutely necessary. Medications in this category include, but are not limited to, glucocorticoids, i.e., high dose oral, parenteral and daily inhaled steroids, and immunosuppressive or cytotoxic drugs. Other than from participation in this study, subjects should not receive experimental agents, including vaccines, for the duration of the study.

The administration of licensed vaccines, should be delayed until 28 days after the last administration of the investigational vaccine.

7 STUDY SCHEDULE

The following sections provide a detailed listing of the procedures and tests to be performed in this study at designated time points. The total volume of blood (approximately 669 mL) to be collected from each volunteer over their 13-month participation in the trial is approximately the volume collected when donating one unit of blood and should not compromise the health of trial subjects. See **Appendix A** for the schedule of study procedures.

7.1 Screening

The following procedures will be performed upon initial screening (note that all procedures might not be performed on the same day):

1. Explain the study and Informed Consent to the volunteer.
2. Ensure the subject has passed the informed consent comprehension questionnaire, has signed the Informed Consent and receives a signed copy of the Informed Consent.
3. Elicit a complete medical history, including medication history, and for female subjects, a menstrual and contraceptive history and/or history of surgical sterility.
4. Administer a physical examination, including vital signs (heart rate, respiratory rate, arterial blood pressure, and oral temperature).
5. Obtain blood for hematology, biochemistry, serologic tests for HIV and viral hepatitis (B and C), and serological tests for IgE antibodies to Na-APR-1 (M74) and Na-GST-1.
6. Obtain fecal sample for examination for ova and parasites.
7. Obtain urine for urine dipstick testing, as well as urine hCG testing in females.
8. Counsel females to avoid becoming pregnant during the vaccination phase of the study.

Screening steps 3-8 must be performed within 90 days before the planned enrollment into the study. Should this screening window be exceeded before the first vaccination, screening procedures (not including administration of the informed consent form or comprehension questionnaire) may be repeated to ensure continued eligibility for the study (screening procedures can be repeated a maximum of one time). Screening laboratory tests (other than serologic tests for HIV, viral hepatitis, and antigen specific IgE antibodies) may be repeated up to one time to confirm any abnormalities.

If the fecal exam performed during screening demonstrates infection with an intestinal parasite the individual will be treated with an appropriate medication prior to being enrolled in the study and before any vaccinations. Individuals infected with *Ascaris lumbricoides*, hookworm or *Trichuris trichiura* will be treated with three daily 400 mg doses of albendazole; individuals infected with *S. mansoni* or *Taenia* spp. will be treated with a single 60 mg/kg oral dose of praziquantel; and, individuals infected with *Strongyloides stercoralis* will be treated with three 400 mg daily oral doses of albendazole.

7.2 Enrollment/Baseline

Volunteers will not be considered enrolled in the study until they have received their first dose of vaccine. In the event that a volunteer is randomized but not enrolled on the day of first vaccination, they will be replaced with an eligible alternate.

Study Day 0 (Day of First Vaccination)

1. Verify that Informed Consent was obtained.
2. Verify that all applicable eligibility criteria have been met.
3. Perform abbreviated history (including concomitant medications) and physical exam, focusing on any acute complaints.
4. Obtain blood for hematology, biochemistry, anti-*Na*-GST-1 and anti-*Na*-APR-1 (M74) antibody assays, and cellular immunology assays.
5. For females, obtain a urine sample for hCG testing. Ensure that test is negative before proceeding; a positive test will exclude the volunteer from the trial.
6. Record vital signs (blood pressure, oral temperature, and heart rate).
7. Administer the vaccine.
8. Observe for at least 1 hour after vaccination to evaluate for immediate adverse reactions. During the 1-hour post-immunization wait period, study staff will discuss signs and symptoms of potential AEs.

7.3 Follow-up

Study Day 1

1. Perform basic history and physical exam (including injection site), emphasizing examination of any acute complaints (i.e., AE data collection).
2. Record vital signs.

Study Day 3 +/- 1

1. Perform basic history and physical exam (including injection site), emphasizing examination of any acute complaints.
2. Record vital signs.

Study Day 7 +/- 1

1. Perform basic history and physical exam (including injection site), emphasizing examination of any acute complaints.
2. Record vital signs.
3. Obtain blood for anti-*Na*-GST-1 and anti-*Na*-APR-1 (M74) antibody assays and cellular immunology assays.

Study Day 14 +/- 2

1. Perform basic history and physical exam (including injection site), emphasizing examination of any acute complaints.
2. Record vital signs.
3. Obtain blood for hematology, biochemistry, anti-*Na*-GST-1 and anti-*Na*-APR-1 (M74) antibody assays, and cellular immunology assays.

Study Day 28 +/- 4

1. Perform basic history and physical exam (including injection site), emphasizing examination of any acute complaints.
2. Record vital signs.
3. Obtain blood for anti-*Na*-GST-1 and anti-*Na*-APR-1 (M74) antibody assays and cellular immunology assays.

Study Day 56 +/- 7 (Day of Second Vaccination)

1. Perform basic history (including concomitant medications) and physical exam (including injection site), emphasizing examination of any acute complaints.
2. Obtain blood for hematology, biochemistry, anti-*Na*-GST-1 and anti-*Na*-APR-1 (M74) antibody assays, and cellular immunology assays.
3. For females, obtain a urine sample for hCG testing. Ensure that test is negative before proceeding; a positive test will exclude the volunteer from further vaccinations.
4. Record vital signs.
5. Administer the vaccine.
6. Observe for at least 1 hour after vaccination to evaluate for immediate adverse reactions.

Study Day 57 (1 day after Second Vaccination)

1. Perform basic history and physical exam (including injection site), emphasizing examination of any acute complaints.
2. Record vital signs.

Study Day 59 (3 +/- 1 days after Second Vaccination)

1. Perform basic history and physical exam (including injection site), emphasizing examination of any acute complaints.
2. Record vital signs.

Study Day 63 (7 +/- 1 days after Second Vaccination)

1. Perform basic history and physical exam (including injection site), emphasizing examination of any acute complaints.
2. Record vital signs.
3. Obtain blood for anti-*Na*-GST-1 and anti-*Na*-APR-1 (M74) antibody assays and cellular immunology assays.

Study Day 70 (14 +/- 2 days after Second Vaccination)

1. Perform basic history and physical exam (including injection site), emphasizing examination of any acute complaints.
2. Record vital signs.
3. Obtain blood for hematology, biochemistry, anti-*Na*-GST-1 and anti-*Na*-APR-1 (M74) antibody assays, and cellular immunology assays.

Study Day 84 (28 +/- 4 days after Second Vaccination)

1. Perform basic history and physical exam, emphasizing examination of any complaints.
2. Record vital signs.
3. Obtain blood for anti-*Na*-GST-1 and anti-*Na*-APR-1 (M74) antibody assays and cellular assays.

Study Day 112 +/- 14 (Day of Third Vaccination)

1. Perform basic history (including concomitant medications) and physical exam (including injection site), emphasizing examination of any acute complaints.
2. Obtain blood for hematology, biochemistry, anti-*Na*-GST-1 and anti-*Na*-APR-1 (M74) antibody assays, and cellular immunology assays.
3. For females, obtain a urine sample for hCG testing. Ensure that test is negative before proceeding; a positive test will exclude the volunteer from further vaccinations.
4. Record vital signs.
5. Administer the vaccine.
6. Observe for at least 1 hour after vaccination to evaluate for immediate adverse reactions.

Study Day 113 (1 day after Third Vaccination)

1. Perform basic history and physical exam (including injection site), emphasizing examination of any acute complaints.
2. Record vital signs.

Study Day 115 (3 +/- 1 days after Third Vaccination)

1. Perform basic history and physical exam (including injection site), emphasizing examination of any acute complaints.
2. Record vital signs.

Study Day 119 (7 +/- 1 days after Third Vaccination)

1. Perform basic history and physical exam (including injection site), emphasizing examination of any acute complaints.
2. Record vital signs.
3. Obtain blood for anti-*Na*-GST-1 and anti-*Na*-APR-1 (M74) antibody assays and cellular immunology assays.

Study Day 126 (14 +/- 2 days after Third Vaccination)

1. Perform basic history and physical exam (including injection site), emphasizing examination of any acute complaints.
2. Record vital signs.
3. Obtain blood for hematology, biochemistry, anti-*Na*-GST-1 and anti-*Na*-APR-1 (M74) antibody assays, and cellular immunology assays.

Study Day 140 (28 +/-4 days after Third Vaccination)

1. Perform basic history and physical exam, emphasizing examination of any acute complaints.
2. Obtain blood for anti-*Na*-GST-1 and anti-*Na*-APR-1 (M74) antibody assays and cellular immunology assays.
3. Obtain stool for examination for ova and parasites.

Study Day 200 (3 months +/-14 days after Third Vaccination)

1. Perform basic history and physical exam, emphasizing examination of any acute complaints.
2. Obtain blood for anti-*Na*-GST-1 and anti-*Na*-APR-1 (M74) antibody assays, and cellular immunology assays.

Study Day 290 (6 months +/-14 days after Third Vaccination)

1. Perform basic history and physical exam, emphasizing examination of any acute complaints.

2. Obtain blood for anti-*Na*-GST-1 and anti-*Na*-APR-1 (M74) antibody assays and cellular immunology assays.

7.4 Final Study Visit

Study Day 380 (9 months +/-21 days after Third Vaccination)

1. Perform basic history and physical exam, emphasizing examination of any acute complaints.
2. Obtain blood for anti-*Na*-GST-1 and anti-*Na*-APR-1 (M74) antibody assays and cellular immunology assays.
3. Obtain stool for examination for ova and parasites.

7.5 Early Termination Visit

The following activities will be performed at the early termination visit for subjects who withdraw, or are withdrawn or terminated from the study:

- Obtain interim medical history by interview of subjects and note any changes since the previous visit.
- All concomitant medications will be recorded on the appropriate data collection form (if within 28 days of subject's last vaccination received in the study).
- Information regarding adverse events/Serious Adverse Events will be assessed and recorded on the appropriate data collection form (adverse events will be limited to new-onset chronic medical conditions and SAEs if after 28 days after the third study vaccination).
- A targeted physical examination may be performed by a study clinician licensed to make medical diagnoses and listed on the Form FDA 1572 as the Principal Investigator or co-investigator, if indicated based on review of interim medical history.
- Approximately 10 mL of venous blood may be collected for safety labs and performed by the local clinical laboratory (if prior to Visit 14 and if not recently obtained per study schedule).
- Approximately 40 mL of venous blood may be collected for antibody and cellular assays (if prior to Visit 14 and if not recently obtained).

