3.2 Study Outcome Measures

3.2.1 Primary Outcome Measures

Safety

The following parameters will be evaluated for each dose and formulation of *Na*-APR-1 (M74) alone or co-administered with *Na*-GST-1:

1. Frequency of solicited injection site and systemic reactogenicity, graded by severity, on the day of each study vaccination through 14 days after each study vaccination.
2. Frequency of study vaccine-related serious adverse events from the time of the first study vaccination through approximately 9 months after the last study vaccination.
3. Frequency of clinical safety laboratory adverse events.
4. Frequency of unsolicited adverse events, graded by severity, from the time of each study vaccination through approximately 1 month after each study vaccination.
5. Frequency of new-onset chronic medical conditions through approximately 9 months after the third study vaccination.
6. Frequency of Adverse Events of Special Interest through approximately 9 months after the third study vaccination.

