7.6 Unscheduled Visit

Unscheduled visits may occur at any time during the study. Any of the following activities may be performed:

- Review concomitant medications (if prior to 28 days after a study vaccination).
- Review adverse events (if prior to 28 days after a study vaccination).

- Review serious adverse events and new-onset chronic medical conditions
- Obtain medical history by interview of subjects and note any changes since the previous visit (if indicated).
- A targeted physical examination may be performed by a study clinician, if indicated based on review of medical history.
- Examine study vaccination site (if within 14 days after a study vaccination).
- Approximately 10 mL of venous blood will be collected for safety labs and performed by the study clinical laboratory (if indicated).

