9 ASSESSMENT OF SAFETY

9.1 Specification of Safety Parameters

Safety will be assessed by the frequency and severity of:

1. Study vaccine-related serious adverse events occurring from the time of the first study vaccination through approximately 12 months after the last study vaccination.
2. Solicited Adverse Events – reactogenicity events occurring on the day of each study vaccination through 14 days after each study vaccination:
 - a) Injection site reactions including erythema (redness), induration (hardness)/swelling, pain, and tenderness.
 - b) Systemic reactions including fever, feverishness (chills/shivering/sweating), fatigue (tiredness), malaise (general unwell feeling), myalgia (body aches/muscular pain exclusive of the injection site), arthralgia (joint pain exclusive of the injection site), headache, and nausea.
3. Clinical safety laboratory adverse events occurring from the time of each study vaccination through approximately 14 days after each set of vaccinations. Parameters to be evaluated include WBC, ANC, hemoglobin concentration, and platelet count; ALT; and, creatinine.
4. Unsolicited Adverse Events – non-serious adverse events occurring from the time of the each study vaccination through approximately 28 days after each vaccination.
5. New-onset chronic medical conditions occurring from the time of the first study vaccination through approximately 9 months after the last study vaccination.
6. Adverse Events of Special Interest occurring from the time of the first study vaccination through approximately 9 months after the last study vaccination.

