9.4 Type and Duration of Follow-up of Subjects after Adverse Events

AEs will be recorded if they start from the time of the first study vaccination (Day 0) up to 28 days after each dose of study product. AEs limited to new-onset chronic medical conditions will be followed through approximately 9 months after the third study vaccination (Day 380).

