9.5 Halting Rules

If a dose of study vaccine is considered significantly reactogenic (see below and Section 9.2.2), dose escalation and/or additional vaccinations will be suspended until reviewed by the SMC, Independent Safety Monitor, DMID Medical Monitor, and IND sponsor (SVI). Any recommendation of the Independent Safety Monitor, DMID Medical Monitor, and SMC to resume or suspend further injections (either for an individual subject, an entire Group, or the full study) will be communicated in writing to the sponsor and Principal Investigator. All communications from the SMC will subsequently be forwarded by the investigators to the IRBs.

The following criteria will be used to define significant reactogenicity:

- One or more participants experience a protocol defined SAE that is determined to be possibly, probably, or definitely related to a study vaccine, **OR**,
- One or more participants experience a protocol defined AESI that is determined to be possibly, probably, or definitely related to a study vaccine, **OR**,
- One or more participants experience a protocol defined Grade 3 hypersensitivity reaction that is possibly, probably or definitely related to a study vaccine, **OR**,
- Two or more participants experience a protocol defined Grade 2 hypersensitivity reaction that is probably or definitely related to a study vaccine, **OR**,
- One or more participants in a single Group (i.e., Group 1, Group 2, etc.) experience the same objective physical finding or laboratory abnormality of Grade 3 or higher (with the exception of isolated Grade 3 erythema or swelling), that is determined to be probably or definitely related to a study vaccine, **OR**,
- Two or more participants in a single Group experience the same Grade 2 or higher safety laboratory abnormality or Grade 3 clinical AE that is possibly, probably or definitely related to a study vaccine.

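### The early-termination visit rule in Section 7.5 leaves out adverse events of special interest after 28 days post dose 3, although they are a primary outcome to Day 380 (minor)

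*Protocol*

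**What the plan says.** **AESIs as an outcome.** Section 3.2.1 makes primary outcome 6 the "Frequency of Adverse Events of Special Interest through approximately 9 months after the third study vaccination". Section 9.1 lists as safety parameter 6 "Adverse Events of Special Interest occurring from the time of the first study vaccination through approximately 9 months after the last study vaccination". Section 11.4 repeats the primary outcome. Vaccine-related SAEs and new-onset chronic conditions are separate items in the same list (outcomes 2 and 5).

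**Early-termination visit.** Section 7.5 requires an interim history and the recording of adverse events, with the limit that "adverse events will be limited to new-onset chronic medical conditions and SAEs if after 28 days after the third study vaccination".

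**Unscheduled visit.** Section 7.6 offers a list of activities that may be performed. General adverse event review is confined to the 28 days after a vaccination. The item without a time limit is "Review serious adverse events and new-onset chronic medical conditions".

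**Other places.** Section 9.4 says that "AEs limited to new-onset chronic medical conditions will be followed through approximately 9 months after the third study vaccination". The protocol summary names new-onset chronic conditions and SAEs for collection to the final visit. Section 5.3.4, on events ongoing at withdrawal, covers all adverse events and gives examples. AESIs are named in none of these three.

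**Scheduled visits.** Appendix A marks a combined AE, SAE and AESI assessment at every scheduled visit from Day 0 to Day 380. It has no column for early-termination or unscheduled visits.

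**The concern.** Section 7.5 does more than fail to mention AESIs. It sets a closed list for the late period, and AESIs are not on it. That conflicts with an outcome that counts AESIs over the same months.

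The two permitted categories do not cover every AESI. The list in Section 9.3.4 includes Bell's palsy, neuritis, reactive arthritis and erythema nodosum, which need be neither chronic nor serious. The important-medical-event route to seriousness in Section 9.2.3 is a matter of judgement.

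The early-termination visit is where the omission counts, because no scheduled visit follows it to ask again. The loss could also be related to the outcome. Section 5.3.3 allows withdrawal for a new clinical finding, so a subject who leaves because of a possible AESI would be seen under the restricted list. AESIs are monitored because of a possible link to an immunostimulatory adjuvant, and so few are expected that each one matters to the count.

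**Working it through.** The plan gives no figure on this point, so the check compares the text and then sizes the gap.

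**1. Who asks about AESIs, by contact, more than 28 days after dose 3 (nominally after Day 140)**

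| Contact | AESIs asked for? | Later scheduled contact? |
|---|---|---|
| Scheduled visits, Days 200, 290, 380 | Yes (Appendix A) | Yes, until Day 380 |
| Unscheduled visit | Not named; list is optional (7.6) | Yes, if the subject stays in |
| Early-termination visit | Excluded by a stated limit (7.5) | No |

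Only the last row combines an exclusion with no later opportunity.

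**2. How long an event can go without a scheduled AESI assessment**

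Nominal intervals from Appendix A: 200 − 140 = 60 days; 290 − 200 = 90 days; 380 − 290 = 90 days. For a subject who attended the preceding scheduled visit, the exposed period before an early-termination visit is therefore at most about 90 days, visit windows aside. The same 90 days is roughly the longest delay for an AESI not recorded at an unscheduled visit.

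**3. Expected number of unrecorded events (assumed inputs)**

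The protocol gives no AESI or dropout rates. Assume:
- AESI risk per subject in the late period, r: 1% to 3%
- share of subjects leaving through an early-termination visit in that period, w: 5% to 20%
- share of AESIs neither serious nor chronic, f: 10% to 30%

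With N = 60, expected events = 60·r·w·f, and the chance of at least one = 1 − (1 − r·w·f)^60.
- Low end: r·w·f = 0.01 × 0.05 × 0.10 = 0.00005. Expected 0.003; chance 0.3%.
- High end: r·w·f = 0.03 × 0.20 × 0.30 = 0.0018. Expected 0.108; chance 10.25%.

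Both ends overstate the route. They count every late AESI in an early leaver as arising after the last scheduled visit, whereas some would already have been recorded.

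**4. Link to the halting rule**

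Section 9.5 includes the criterion "One or more participants experience a protocol defined AESI that is determined to be possibly, probably, or definitely related to a study vaccine". It suspends escalation or further vaccination, so it matters here only while someone is still to be vaccinated. Assume the last subject enrols 60 to 90 days after the first, in line with the projected 3-month enrolment in Section 4. The last third dose then falls at calendar day 60 + 112 = 172 to 90 + 112 = 202. The first subject reaches Day 140 some 172 − 140 = 32 to 202 − 140 = 62 days earlier. For the last subject the overlap is nil.

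**The case against.** The strongest reply is that AESIs run as their own stream. Section 9.1 separates them from unsolicited events, Section 9.3.3 has them reported by the SAE procedure, and Sections 8.1 and 9.3.4 call for special attention to them. Section 8.1 also requires any event brought to a clinician to be charted, and Section 9.3.5 asks for medically attended events outside scheduled visits to be recorded. On this reading the limit in Section 7.5 was meant for general adverse events, and an AESI found in the interim history would be recorded anyway. That may well be the intention. But reporting duties begin only once an event has been identified and recorded, and general calls for attention do not displace a specific limit on what a particular visit records.

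Other parts of the reply stand:
- **Unscheduled visits.** The Section 7.6 list is optional, and a subject who stays in the study is asked about AESIs at the next scheduled visit. The effect is mainly delay.
- **Section 9.4.** It does not mention SAEs at all. Read as a closed collection list, it would bar late SAEs as well, against Sections 3.2.1 and 9.1. It is weak evidence of an exclusion.
- **Section 5.3.4.** Its list is illustrative and does not shut AESIs out.
- **Which AESIs escape.** The protocol sets no duration for chronic, so this is partly a clinical judgement.

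A reader might infer from Day 140 to Day 380 (240 of 380 days, 63%) that AESI collection lapses for most of follow-up. It does not: the scheduled visits in that period all assess AESIs. A reader might also note that one missed event among the 30 GLA-AF recipients turns 1/30 into 0/30. That is true of any missed event and does not measure this gap.

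**Conclusion.** The contradiction is real and lies in Section 7.5. Its late limit excludes AESIs that a primary outcome counts to about 9 months after dose 3, and Appendix A does not cover the visit concerned. An AESI that is neither chronic nor serious and arises after the last scheduled visit can be lost at the subject's final contact.

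The size is minor. The loss requires early withdrawal in the late period, an event of that kind since the last scheduled visit, and staff applying the limit literally. On the assumed ranges the expected number is well below one, and those ranges are illustrations, not protocol figures.

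A reader might infer that the single-case halting rule is broadly compromised. The protocol does not support that: the link is secondary, confined to roughly the first 32 to 62 days after the earliest subjects pass Day 140 under the enrolment assumption, and absent for the last subjects. No sample-size figure changes.

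**What to change.** In Section 7.5, add AESIs to the categories recorded at an early-termination visit more than 28 days after dose 3. This is the change that matters.

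For consistency, name AESIs without a 28-day limit in Section 7.6, in Section 9.4, among the examples in Section 5.3.4 and in the protocol summary's statement of what is collected to the final visit. All would then agree with Sections 3.2.1 and 9.1 and with Appendix A.

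The cost is wording in these places and one item on the visit form. No visit, blood sample, analysis or safety rule changes.
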